### 2.1 Data analysis general information

Data will be analyzed by Novartis Oncology Biostatistics and Statistical Programming personnel according to the data analysis section 10 of the study protocol as detailed in this analysis plan.

SAS® version 9.4 (or later version if available at time of database lock) will be used for all analyses. Data from all patients who signed informed consent and who received granule treatment will be used in the analysis. Data collected after patients' withdrawal of informed consent for further participation in the study will not be reported (except for death date which might be obtained from public records per local laws).

All statistical analyses will be performed using all data (for patients who received granule treatment) collected in the database up to the last patient last visit (LPLV) date.

All events with a start date before or on the LPLV date and not having documented end date will be reported as 'ongoing'. This approach applies to adverse event and concomitant medication reports. For these events, the end date will not be imputed and therefore will not appear in the listings.

The time periods defined in [Table 2-1](#) will be used to define the extension phase for the analysis.

**Table 2-1      Definition of core and extension phases**

[figure not shown]
Core phase			Extension phase		
Treatment	Start date	Stop date	Treatment	Start date	Stop date
Granules	Date of first IC signed	Date of last treatment of granules + 30 days	No treatment	Nil	Nil
DT	Date of first IC signed	Date of last treatment of DT + 30 days	No treatment	Nil	Nil
Granules	Date of first IC signed	date of first administration of granules in extension phase* – 1 day	Granules	date of first administration of granules in extension phase*	Date of the last administration of Granules in extension + 30 days
DT	Date of first IC signed	Date of first administration of granules* – 1 day	Granules	Date of first administration of Granules*	Date of the last administration of Granules in extension + 30 days

\*including 0 doses for patients to identify the extension start date only

Summaries will be based on:

- Entire granule period - patients randomized to Granules combining core and extension phases (dark green rectangle in [Figure 2-1](#)) side-by-side with Granules for patients randomized to DT who switched to Granules in extension phase (light green rectangle in [Figure 2-1](#)). Cross-over treatment group corresponds to the patients randomized to DT who switched to Granules in the extension phase.

**Figure 2-1      Core and extension phases**

### 2.1.1      General analysis conventions

**Pooling of centers:** Unless specified otherwise, data from all study centers will be pooled for the analysis. Due to expected small number of patients enrolled at centers, no center effect will be assessed.

**Qualitative/categorical data** (e.g., sex, race) will be summarized by frequency counts and percentages. Percentages will be calculated using the number of patients in the relevant treatment arm as the denominator.

**Continuous data** (e.g., age, body weight) will be summarized using appropriate descriptive statistics (i.e. mean, standard deviation, median, minimum, and maximum) by treatment arm. Lower and upper quartiles will also be presented when applicable.

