## Amendment 6 (24-Jun-2021)

### Amendment rationale

As of 24-Jun-2021, 67 patients are ongoing in the extension phase of the study. All patients had completed the Core phase of the study by 18-Dec-2018. The primary analysis for this study was completed on 07-Dec-2018 (data cut-off date 31-May-2018).

The main purpose of this amendment is to introduce the requirement for central collection and assessment of photographs from ocular examinations (lens photographs and wide angle fundus photographs) collected during the study by a Novartis designated imaging Contract Research Organization (CRO). This change is in response to a Health Authority request to submit CALYPSO ophthalmic data (for up to 2 years of follow up) to support the ocular safety evaluation of deferasirox.

Clarification was also added to state that for patients who need correction, the best corrected visual acuity should be tested when performing the distance visual acuity test and that the corrected visual acuity should be documented in the source records.

In addition, mitigation procedures have been implemented throughout the protocol to ensure participant safety and trial integrity during a Public Health emergency, as declared by Local or Regional authorities i.e. pandemic, epidemic or natural disaster.

Finally, assessment of the study Risk/Benefit in light of the ongoing coronavirus disease 2019 (COVID-19) pandemic at the time of this protocol amendment concluded that there are no additional risks related to COVID-19 for this study. Patient with cytopenias are more susceptible to infections in general, compared to patients without cytopenias. There have been postmarketing reports of cytopenias in patients treated with deferasirox and patients with cytopenias may be at higher risk of COVID-19 with a poorer prognosis. The periodic monitoring of blood counts and interruption of study treatment in patients who develop unexplained cytopenia, as defined in the protocol, are expected to mitigate this risk.

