**Figure 2-1      Core and extension phases**

## General analysis conventions

**Pooling of centers:** Unless specified otherwise, data from all study centers will be pooled for the analysis. Due to expected small number of patients enrolled at centers, no center effect will be assessed.

**Qualitative/categorical data** (e.g., sex, race) will be summarized by frequency counts and percentages. Percentages will be calculated using the number of patients in the relevant treatment arm or subgroup as the denominator.

**Continuous data** (e.g., age, body weight) will be summarized using appropriate descriptive statistics (i.e. mean, standard deviation, median, minimum, and maximum) by treatment arm. Lower and upper quartiles will also be presented when applicable.

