### **2.2 Analysis sets**

The Safety Set 1 will consist of all ICT naïve patients (as per eCRF) who received at least one dose of the study drug during the core phase.

The Safety Set 2 will consist of all ICT pre-treated patients (as per eCRF) who received at least one dose of study drug during the core phase.

The Safety Set 3 will consist of all patients who received at least one dose of study drug during the core phase.

Safety set 1 to 3 will only be used for the analysis of lens photography (LOCSIII) and color fundus photography. Safety set 3 is only used for disclosure related analysis, deaths and drug

dispensation listings. Both assessments were only collected since protocol amendment 6 which was implemented after the EoC CSR.

All analysis for the final CSR will be based on Safety Set 4.

The Safety Set 4 will consist of all patients who received at least one dose of granule formulation during the core or extension phase.

Patients will be analyzed according to the treatment actually received and strata information recorded in the eCRF.

Treatment actually received is defined as the treatment the patient received at the first day of study medication in the core phase

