#### **2.7.6.2 Slit lamp**

For each considered evaluation type in the CRF page and eye side, the number & percentage of subjects with and without abnormality (normal, insignificant, clinically significant) will be provided by timepoint and treatment arm. In addition, for each slit lamp evaluation, shift tables will be generated to present the worst post-baseline changes compared to baseline by treatment arm and eye side. Further, shift tables will be generated by visit, treatment arm and eye side. A listing of patients with any abnormality will be provided.

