### **2.7.6.6 Color Fundus Photography**

The Color Fundus Photography Assessment will be conducted by a central vendor through photographs. For each considered evaluation type and eye side, the number & percentage of subjects with and without abnormality will be provided by timepoint and treatment arm. For each considered evaluation type and eye side, the number & percentage of subjects for image quality will be provided by timepoint and treatment arm. A listing of subjects will be provided, additionally, listings for the findings, general comments and confidence score comments will be presented for safety set 3. As data was not analyzed so far, the analysis will be repeated for safety set 1 to 3.

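### By-visit ocular abnormality percentages in the final SAP are taken over the whole arm, so they are diluted by the share of children actually assessed

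*SAP*

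**What the plan says.** The general conventions in the final SAP (2.1.1) fix the denominator for categorical data: "Percentages will be calculated using the number of patients in the relevant treatment arm as the denominator". The primary-analysis SAP has nearly the same sentence, allowing an arm or a subgroup: "Percentages will be calculated using the number of patients in the relevant treatment arm or subgroup as the denominator". Neither refers to the number assessed.

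The ocular sections of the final SAP then ask for percentages at each visit. For slit lamp (2.7.6.2), subjects "with and without abnormality (normal, insignificant, clinically significant) will be provided by timepoint and treatment arm". Fundus oculi (2.7.6.5) follows the same pattern. For colour fundus photography (2.7.6.6), "the number & percentage of subjects with and without abnormality will be provided by timepoint and treatment arm". None of these sections replaces the general denominator.

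The main population is broad (2.2): "The Safety Set 4 will consist of all patients who received at least one dose of granule formulation during the core or extension phase". Section 2.1 shows it in two columns: patients randomised to granules, over core and extension together, beside patients randomised to DT who switched to granules in the extension. The centrally read lens and fundus photographs are also analysed on Safety Sets 1 to 3.

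Section 2.7.6 separately requires the frequency and percentage of subjects with completed ocular assessments by eye side, evaluation type, timepoint and arm.

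**The concern.** A by-visit percentage is naturally read as the proportion of examined children who had an abnormality. Under the stated rule it is that proportion multiplied by the proportion examined. The printed figure can only be lower than or equal to the rate among those examined, and it falls as fewer children attend, even if the underlying rate is constant or rising.

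Two features make this matter for ocular safety. The extension runs for up to five years, so the share assessed is likely to be lowest when cumulative exposure is longest. And the two Safety Set 4 columns lose patients differently: a granule patient who left in the core phase stays in the granule denominator at every extension visit, while a DT patient who left in the core phase was never in the crossover column. Equal true rates can then print as unequal percentages.

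The central reading of photographs was added because a Health Authority asked for ophthalmic data (protocol, Amendment 6 rationale), so these tables will be read closely.

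**Working it through.** The documents state no ocular rate, assessed count or Safety Set 4 size, so there is no planned figure to reproduce. The check is direct arithmetic on the rule.

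**Inputs**
- Denominator N: all patients in the arm (final SAP 2.1.1). For illustration N = 108, the planned maximum per group (protocol 10.8); it is not the size of a Safety Set 4 column.
- Number assessed n and number abnormal x: not in the documents. Assumed: share n/N from 100% down to 25%, and a rate x/n of 10%, with 5% and 20% as alternatives.

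**Formula**

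Printed % abnormal = x/N = (x/n) × (n/N)

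Printed % without abnormality = (n − x)/N = (1 − x/n) × (n/N)

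In neither row = (N − n)/N

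**Result for an assumed 10% rate, N = 108**

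| Share assessed | n | x (expected) | Printed % with (x/108) | Printed % without | In neither row | % with among assessed (x/n) |
|---|---|---|---|---|---|---|
| 100% | 108 | 10.8 | 10.0% | 90.0% | 0% | 10% |
| 75% | 81 | 8.1 | 7.5% | 67.5% | 25% | 10% |
| 50% | 54 | 5.4 | 5.0% | 45.0% | 50% | 10% |
| 25% | 27 | 2.7 | 2.5% | 22.5% | 75% | 10% |

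At 50% assessed, an assumed 5% prints as 2.5% and an assumed 20% as 10%. The relative dilution depends only on n/N, not on the rate or on N.

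**Between columns.** Suppose the true rate is 10% in both columns at an extension visit, with 50% of the granule column and 75% of the crossover column assessed. The table prints 5.0% and 7.5%. The 2.5-point gap comes from the denominators alone.

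**How low could the share go?** The Amendment 6 rationale reports "67 patients are ongoing in the extension phase of the study" at 24 June 2021. Against planned maxima, 67/216 = 31% if every DT patient had switched to granules, and 67/108 = 62% if none had. These are rough bounds on the share of Safety Set 4 still on treatment then, not counts of children examined or imaged at any visit.

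**Which outputs are affected**
- By-timepoint slit lamp, fundus oculi and colour fundus percentages: fully.
- Any percentages in by-visit shift tables (acuity, slit lamp, tonometry): the same mechanism.
- Lens photography (2.7.6.4): grades appear as a worst-change shift table; only image quality is by timepoint.
- End-of-treatment and worst-post-baseline tables: section 5.3.4 carries the last on-treatment value forward for the first and uses all on-treatment values for the second. Neither shrinks visit by visit, although patients never assessed still dilute any percentage in them.

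**The case against.** The strongest reply is that the plan already discloses what is needed. Section 2.7.6 tabulates completed assessments by eye, type, timepoint and arm, and the abnormality tables give counts, so a reader can divide one by the other. The outputs are descriptive, Table 4-1 says no comparison between the two granule groups is planned, a fixed arm denominator is a common convention, and the table shells, which are separate documents, may handle this. Most of that stands and is why the point is minor. It does not remove the point. A completed assessment is not necessarily a gradable one, no output is promised for the number evaluable at both baseline and post-baseline, and the printed percentage would still be the diluted one. The authors do depart from full-set summaries elsewhere: the weekly diary rates use non-missing days, and the dose summaries in final SAP 2.4.1 are limited to patients with complete dosing dates.

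Three stronger readings might be inferred, and the documents do not support them.
- **Unexamined children are counted as normal.** They are not. The normal or without-abnormality row is tabulated explicitly and shrinks by the same factor; the rows add to less than 100%, which leaves the missing share visible.
- **Every percentage in the final SAP is affected.** The complete-dates restriction in 2.4.1 alone shows otherwise.
- **Central reading covers only the 67 patients then ongoing, about 33 per arm, so rates are understated about threefold.** Final SAP 2.2 invites this: "Both assessments were only collected since protocol amendment 6 which was implemented after the EoC CSR". But protocol 7.2.4.5 requires screening and on-study photographs taken before Amendment 6 to be sent as well, and Table 7-3 lists screening, Week 25 and end of core. The number with images is unknown, so no such factor can be derived.

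**Conclusion.** Wrong as written, and minor. The final SAP states a denominator rule, and nothing in section 2.7.6 overrides it. Applied literally, it prints by-visit ocular abnormality percentages equal to the rate among assessed children times the share assessed. The direction is certain: downward wherever anyone is unassessed. The size is not known. With an assumed 10% rate it is a fall to 7.5% at 75% assessed and to 5.0% at 50%; the real shares and rates are not in the documents. That the dilution grows at later visits assumes the share assessed declines with follow-up. That it differs between the Safety Set 4 columns rests on the granule column including patients who never entered the extension. The required table of completed assessments limits the harm to a misleading printed percentage that a careful reader can largely correct.

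**What to change.** Add to final SAP 2.7.6, as an exception to 2.1.1:
- By-timepoint ocular percentages use as denominator the patients with an evaluable assessment (for photographs, a gradable one) of that type and eye at that timepoint.
- Shift-table percentages, including the lens-opacity worst-change shifts, use patients with both a baseline and a post-baseline evaluable assessment of that type and eye.
- That n is printed beside the arm total in each table.

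Apply this to Safety Set 4 and to the repeats of the photograph analyses on Safety Sets 1 to 3, and align the table shells.

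The cost is one short passage of text and a denominator variable. Completed assessments are already to be counted; the gradable and paired baseline/post-baseline counts need a further derivation. No new data are required.

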### **2.1.2 Study drug and study treatment**

The terms study drug and study treatment are equivalent and will refer to deferasirox granule.

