Stop study participation	Point/time at which the patient came in for a final evaluation visit or when study treatment was discontinued whichever is later
Study treatment	Includes any drug or combination of drugs in any study arm administered to the patient as part of the required study procedures, including placebo and active drug run-ins.
Study treatment discontinuation	Point/time when patient permanently stops taking study treatment for any reason; may or may not also be the point/time of premature patient withdrawal
Treatment group	A treatment group defines the dose and regimen or the combination, and may consist of 1 or more cohorts. Cohorts are not expanded, new cohorts are enrolled.
Variable	Identifier used in the data analysis; derived directly or indirectly from data collected using specified assessments at specified time points

---

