### Study drug and study treatment

The terms study drug and study treatment are equivalent and will refer both to deferasirox DT or deferasirox granule.

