### **Study drug and study treatment**

The terms study drug and study treatment are equivalent and will refer both to deferasirox DT or deferasirox granule.

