#### **2.7.3 Disclosure related analysis**

In order to provide a cumulative summary of AEs by treatment arm and by phase (core, extension) during the study for disclosure, the following arms need to be generated within a single XML file based on safety set 3.

- Deferasirox DT: CORE
- Deferasirox granules: CORE
- Deferasirox granules: Extension (including patients who already received granules in the core phase)
- Crossover to Deferasirox granules: Extension (including patients who received DT in core phase but crossed over to deferasirox granules during the extension phase)

For the legal requirements of ClinicalTrials.gov and EudraCT, two required tables on on-treatment adverse events which are not serious adverse events with an incidence greater than 5% and on on-treatment serious adverse events and SAE suspected to be related to study treatment will be provided by system organ class and preferred term on the safety set population.

If for a same patient, several consecutive AEs (irrespective of study treatment causality, seriousness and severity) occurred with the same SOC and PT:

- a single occurrence will be counted if there is  $\leq 1$  day gap between the end date of the preceding AE and the start date of the consecutive AE
- more than one occurrence will be counted if there is  $> 1$  day gap between the end date of the preceding AE and the start date of the consecutive AE

For occurrence, the presence of at least one SAE / SAE suspected to be related to study treatment / non SAE has to be checked in a block e.g., among AE's in a  $\leq 1$  day gap block, if at least one SAE is occurring, then one occurrence is calculated for that SAE.

The number of deaths resulting from SAEs suspected to be related to study treatment and SAEs irrespective of study treatment relationship will be provided by SOC and PT.

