**Table 2-2 Standard grades for LOCSIII assessment**

Nuclear Color (NC)	Nuclear Opalescence (NO)	Cortical (C)	Posterior Subcapsular (P)
No Opacity is $\geq 0.1$ to $<1$			
NC1 is $\geq 1$ to $<2$	NO1 is $\geq 1$ to $<2$	C1 is $\geq 1$ to $<2$	P1 is $\geq 1$ to $<2$
NC2 is $\geq 2$ to $<3$	NO2 is $\geq 2$ to $<3$	C2 is $\geq 2$ to $<3$	P2 is $\geq 2$ to $<3$
NC3 is $\geq 3$ to $<4$	NO3 is $\geq 3$ to $<4$	C3 is $\geq 3$ to $<4$	P3 is $\geq 3$ to $<4$
NC4 is $\geq 4$ to $<5$	NO4 is $\geq 4$ to $<5$	C4 is $\geq 4$ to $<5$	P4 is $\geq 4$ to $<5$
NC5 is $\geq 5$ to $<6$	NO5 is $\geq 5$ to $<6$	C5 is $\geq 5$ to $\leq 5.9$	P5 is $\geq 5$ to $\leq 5.9$
NC6 is $\geq 6$ to $\leq 6.9$	NO6 is $\geq 6$ to $\leq 6.9$		

The worst change in grade compared to baseline for each eye, evaluation type, and treatment arm will also be presented using shift tables. For each considered evaluation type and eye side, the number & percentage of subjects for image quality will be provided by timepoint and treatment arm. A listing of subjects will be provided, additionally, listings for the findings, general comments and confidence score comments will be presented for safety set 3. As data was not analyzed so far, the analysis will be repeated for safety set 1 to 3.

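### The final SAP defines study drug as granules only, yet assigns outputs that need DT patients to Safety Sets 1 to 3, which are defined by that same term

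*SAP*

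**What the plan says.** **The term.** Final SAP 2.1.2: "The terms study drug and study treatment are equivalent and will refer to deferasirox granule". The primary SAP (Amendment 3) and the End-of-Core SAP, both in section 2.6, had: "The terms study drug and study treatment are equivalent and will refer both to deferasirox DT or deferasirox granule". The protocol glossary is broader still for study treatment: "Includes any drug or combination of drugs in any study arm administered to the patient as part of the required study procedures".

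**The data restriction.** Final SAP 2.1: "All statistical analyses will be performed using all data (for patients who received granule treatment"), up to the last patient's last visit. The text under Table 2-1 then bases the summaries on the entire granule period.

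**The sets.** Final SAP 2.2: "The Safety Set 3 will consist of all patients who received at least one dose of study drug during the core phase". Safety Sets 1 and 2 use the same condition for ICT-naïve and pre-treated patients. Protocol 10.1.2 instead defines these sets by any dose of study medication in the core phase.

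**The outputs placed on those sets in the final SAP.**
- Lens photography (LOCSIII, 2.7.6.4) and colour fundus photography (2.7.6.6), each with the sentence "As data was not analyzed so far, the analysis will be repeated for safety set 1 to 3".
- The listing of all deaths (2.7.2) and the drug dispensing listing (2.4), both on Safety Set 3.
- Adverse-event disclosure (2.7.3): "the following arms need to be generated within a single XML file based on safety set 3". The four arms are DT in the core phase, granules in the core phase, granules in the extension, and DT patients who crossed over to granules in the extension.

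Table 4-1, which declares changes from the protocol, lists only the dropped exposure-adjusted adverse-event incidence.

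**The concern.** One sentence was narrowed to suit a report that is mostly about the granule period, while the set definitions built on it kept their old wording. Put the new meaning into the old definitions and the three sets lose the DT arm, although several outputs were assigned to them in order to show both formulations.

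The lens and fundus readings matter most. Table 1-1 of the final SAP lists them under the core-phase objective on the safety of both formulations and says that they will appear in this report. Section 2.7.6 says that they have never been reported. Protocol 7.2.4.5 sends all screening and on-study photographs for central reading, including those taken before Amendment 6, and protocol Table 7-3 schedules core-phase photographs at screening, Week 25 and end of core. DT core-phase images are therefore within the plan, and no earlier report covers their central reading.

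**Working it through.** No power or error-rate figure bears on this. The check is to substitute the definition, follow the dates, and see what is left.

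**1. Set membership.** Patients in the DT arm take only DT in the core phase. If study drug means granules, a core-phase dose of study drug excludes them, barring dispensing errors. Planned ceilings from protocol 10.8 are 96/2 = 48 naïve and 120/2 = 60 pre-treated per arm, so 48 + 60 = 108 per arm.

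| Set | DT or granules | Granules only | DT patients under granules only |
|---|---|---|---|
| Safety Set 1 | 48 + 48 = 96 | 48 | 0 |
| Safety Set 2 | 60 + 60 = 120 | 60 | 0 |
| Safety Set 3 | 108 + 108 = 216 | 108 | 0 |

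Two of the four disclosure arms (DT in core, crossover in extension) would be empty.

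**2. The data restriction acts separately.** A DT patient who never entered the extension received no granules. Section 2.1 removes that patient's data whatever Safety Set 3 means, so correcting 2.1.2 alone is not enough.

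**3. Dates for DT-only patients.** Section 2.1.3 takes the first non-zero dose of study drug. Under 2.1.2 such a patient has none, so study day (2.1.4), baseline (2.1.5) and the on-treatment period (2.1.6) have no starting point.

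**4. Dates for switchers.** Study Day 1 becomes the first granule dose. Assume that granules start at Visit 17 (Week 49), as scheduled in protocol Table 7-2. On the randomisation scale:
- Week 25 is day 24 × 7 + 1 = 169.
- Week 49 is day 48 × 7 + 1 = 337.
- By the formula in 2.1.4 for assessments before treatment start, the Week 25 photograph falls on study day 169 − 337 = −168.

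Table 5-6 places everything up to Study Day 1 in the baseline window and reserves Study Days 140 to 197 for Week 25. The DT-period Week 25 photograph therefore lands in the baseline window. The end-of-core photograph, due on the day granules start, falls on Study Day 1: it is in the baseline window and is also named for the end-of-core row. Worst post-baseline values use on-treatment data only (5.3.4), so the Week 25 photograph cannot count there either.

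**5. What remains under the literal reading.** Switchers' granule-period images and events stay, through Safety Set 4. What is lost is DT core-phase follow-up as a comparator, and every DT patient who never took granules.

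**The case against.** The strongest reply is that the final SAP cannot mean what 2.1.2 literally says.
- Section 2.7.3 requires a DT core-phase arm from Safety Set 3, which cannot be built from a set without DT patients.
- Section 2.4.1 speaks of the last exposure to study drug in the core phase for patients who were then on DT.
- Table 2-1 keeps a row for DT patients who never received granules.
- If Safety Set 3 held only core-phase granule recipients, it would be a subset of Safety Set 4, and there would be little reason to list all deaths on it or to add lens and fundus analyses for it.
- Section 2.1 refers to protocol section 10, whose Safety Set 3 includes DT, and the earlier SAPs are named as references.

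This stands as evidence of intent. A reader might infer that DT was deliberately removed, or that it will certainly drop out; the documents do not support either.

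Intent does not finish the job, however. It does not lift the explicit restriction in 2.1. Table 2-1 gives a DT-only patient a phase that runs from consent to 30 days after the last DT dose, but no first-dose date from which to count study day or on-treatment time. The separate pre-granule baseline for switchers is limited to the entire granule period, but the general baseline rule in 2.1.5 inherits the same narrowed term. The deaths listing needs no time window, because 2.7 lists all data regardless of period; it does need DT patients in the set.

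The reply is also right about consequences. DT core-phase adverse events and deaths were planned on Safety Set 3 in the primary SAP (2.9.2) and the End-of-Core SAP (2.9.6), and all patients had completed the core phase by 18-Dec-2018 (protocol, Amendment 6 rationale). The lens and fundus outputs are descriptive, with no hypothesis test.

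**Conclusion.** The final SAP contradicts itself on DT patients and should be corrected. Followed literally, its rules leave no usable DT arm in the outputs on Safety Sets 1 to 3. Read for intent, they leave the programmer to choose between an explicit definition and an implied one, with the dates unresolved.

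The main exposure is the DT core-phase comparator for the centrally read lens and fundus photographs. The disclosure arms and the deaths and dispensing listings are affected in the same way. For deaths, 2.7.2 ties only the listing to Safety Set 3.

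Three stronger inferences should not be drawn:
- **That deaths and adverse events under DT would go unreported.** Earlier reports were planned to contain them; what is at risk is their place in the final listing and the cumulative disclosure tables.
- **That a health authority asked for a randomised ocular comparison.** The Amendment 6 rationale describes a request for ophthalmic data, up to two years of follow-up, to support the ocular safety evaluation of deferasirox.
- **That about 105 patients are lost.** Half of the 210 randomised by 06-Dec-2017 is 105, but that is an enrolment count, not a count of treated or imaged patients.

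The planned ceiling is 108 DT patients. The number with readable core-phase images is not in the documents; the final SAP plans only a listing of patients with available images.

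**What to change.** Amend the final SAP in three places.
1. In 2.1.2, limit the granule-only meaning of study drug to Safety Set 4 and the entire granule period. For outputs on Safety Sets 1 to 3, restore the meaning in End-of-Core SAP 2.6, where the terms "will refer both to deferasirox DT or deferasirox granule".
2. In 2.1, including the text under Table 2-1, limit the granule-recipient and entire-granule-period restrictions to Safety Set 4 outputs.
3. In 2.1.3 to 2.1.6 and 5.3.4, state that core-phase analyses on Safety Sets 1 to 3 count baseline, study day and the on-treatment period from the first core-phase dose, using the End-of-Core on-treatment rules (End-of-Core SAP 2.9.6). The extension disclosure arms can keep the extension start dates in Table 2-1.

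The cost is a few sentences. The wording and the core-phase rules already exist in the earlier SAPs, and no new data are needed.
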